## Preoperative planning

Planning of the surgery includes planned implant placements and levels of surgery on an AP and sagittal x-ray or preoperative low-dose CT. Operative planning is an important part of all surgeries that will be specifically documented before surgery. Planning includes the specification of each vertebra and pedicle that will be used for implant placement and is documented on a specific protocol before surgery called “Operation protocol MISCOS clinical trial” (see Appendix).

## **Primary endpoint**

The primary endpoint is the assessment of a group of variables by the statistical method of “win odds”. The variables are in hierachic order:

- i. No reoperations at 2 years after surgery. A reoperation is defined as a secondary surgical procedure related to the index procedure and involving the spine at any level after the index procedure.
- ii. No serious complication related to the procedure. Serious complication is defined as a life-threatening complication or a complication related to substantial invalidity (like pneumothorax or spinal cord injury).
- iii. No early surgical site infection (SSI). Early SSI is defined as SSI with onset up to 12 weeks postoperatively.
- iv. No other infection related to the inpatient stay like pneumonia or urinary tract infection (UTI).
- v. Assessment of pain at 2 years f-u: The numeric rating scale (NRS) for back pain will be used measured on a scale from 0 (no pain) to 10 (worst possible pain). Data will be collected from Swespine or similar platforms.
- vi. Assessment of SRS-22r: The SRS-22r is a scoliosis specific questionnaire aiming to estimate quality of life in patients with scoliosis [1]. It contains 24 items divided into 5 domains covering function, pain, self-image, mental health, and satisfaction. An index value is calculated for each domain and a total index value is possible to calculate ranging from 1 (worst) to 5 (best). SRS-22r will be collected from Swespine or similar platforms at 2 years.
- vii. Radiologically healed fusion at 2 years f-u. A radiologically healed fusion is defined as bone bridging along the originally operated levels. A vertebral segment will be considered fused if one or both of the following conditions is satisfied:
  - a. Bone bridge over at least one facet joint
  - b. Bone bridge between the vertebral bodies

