### 5.1 Minimal invasive scoliosis surgical correction- intervention group

Patients operated with MIS: Minimal invasive surgery. The surgeon will be free to choose the method of screw placement. 3D-navigation, RAS, free hand technique or combinations

Clinical Study Protocol	Unique protocol ID	MISCOS
	Version No:	1.1
	Date:	2025-09-27

of these may be used for screw placement. A long skin incision and subcutaneous multiple short incisions are performed. The erector spinae musculature is not detached from the spinous processes and the laminae, except for the exposure needed for the actual screw insertion. Each screw is inserted through an incision in the musculature. After placement of the screws, the positioning is checked with an intraoperative computed tomography. Misplaced screws may be repositioned or extracted. After implant placement, rods are bent to the desired shape and placed. Correction of the deformity and fixation is performed.

The surgeon may choose to do decortication of all or some of the facet joints in the surgical area. Decortication is performed by a navigated high-speed burr or other technique in a minimally invasive way. Finally, the wound/s is/are closed.

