## 5.2 Open scoliosis surgical correction- control group

Patients operated with open surgery: Traditional open surgery. The surgeon will be free to choose the method of screw placement. 3D-navigation, RAS, free hand technique or combinations of these may be used for screw placement. A long skin and subcutaneous incision is performed. The posterior elements of the spine are exposed and the spinal musculature is detached from the posterior elements of the spine. The whole surgical area is exposed and all screws are inserted through this area. Separate incisions for screw placement in the musculature are not needed. After placement of the screws, the positioning is checked with an intraoperative computed tomography. Misplaced screws may be repositioned or extracted. After implant placement, rods are bent to the desired shape and placed. Correction of the deformity and fixation is performed. The surgeon may choose to do decortication of all or some of the facet joints in the surgical area. The surgeon may choose to do decortication of the spinous processes and laminae in the surgical area. Decortication is performed by a high-speed burr or other technique. Finally, the wound is closed.

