## 5.8 Imaging

Normal imaging and time points are as follows: Standard preoperative investigations include a whole spine standing radiograph, a whole spine bending radiograph and magnetic resonance imaging (MRI) of the spine. A preoperative low-dose CT or an intraoperative CBCT is always performed prior to screw placement. Screw placement is verified by a CBCT intraoperatively. The minimum radiologic follow-up includes a whole spine standing radiograph at the 3-month follow-up and a low-dose CT along with a standing radiograph at the 2-year follow-up. Curve size, type of scoliosis and other radiological parameters will be registered.

Clinical Study Protocol	Unique protocol ID	MISCOS
	Version No:	1.1
	Date:	2025-09-27

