## 6 STUDY MEASUREMENTS AND VARIABLES

### 6.1 Primary variables

1. Reoperation within 2 years: A reoperation is defined as a secondary surgical procedure related to the index procedure and involving the spine at any level after the index procedure.
2. Serious complication: A life-threatening complication or a complication related to substantial invalidity (like pneumothorax or spinal cord injury).
3. Early SSI. It is defined as SSI with onset up to 12 weeks postoperatively.
4. Other systemic infection related to inpatient stay: Like pneumonia or UTI
5. Pain at 2 years f-u will be assessed with the numeric rating scale (NRS) for back pain measured on a scale from 0 (no pain) to 10 (worst possible pain). Data will be collected from Swespine or similar platforms.
6. SRS-22r: The SRS-22r is a scoliosis specific questionnaire aiming to estimate quality of life in patients with scoliosis [1]. It contains 24 items divided into 5 domains covering function, pain, self-image, mental health, and satisfaction. An index value is calculated for each domain and a total index value is possible to calculate ranging from 1 (worst) to 5 (best). SRS-22r will be collected from Swespine or similar platforms.
7. Radiologically healed fusion: A radiologically healed fusion is defined as bone bridging along the operated levels according to the preoperative plan. A vertebral segment will be considered fused if one of the following conditions is satisfied:
  - a. Bone bridge over at least one facet joint
  - b. Bone bridge between the vertebral bodies

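### The fusion definition leaves out laminar and spinous-process bridging, a fusion bed that only the open arm may prepare, so the fusion component can lean towards MIS

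*Protocol*

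**What the plan says.** **Fusion definition.** Under Primary endpoint in section 2.1, item vii, the protocol states "A vertebral segment will be considered fused if one or both of the following conditions is satisfied". The conditions are (a) "Bone bridge over at least one facet joint" and (b) "Bone bridge between the vertebral bodies". Section 6.1, item 7, repeats the rule in slightly different words, "A vertebral segment will be considered fused if one of the following conditions is satisfied", with the same two sites. Neither place mentions laminae or spinous processes.

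**MIS arm (5.1).** On exposure: "The erector spinae musculature is not detached from the spinous processes and the laminae, except for the exposure needed for the actual screw insertion". On decortication: "The surgeon may choose to do decortication of all or some of the facet joints in the surgical area". No other decortication site is named.

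**Open arm (5.2).** The same facet-joint permission is given, and then: "The surgeon may choose to do decortication of the spinous processes and laminae in the surgical area". The control-arm description in 2.1 names facet joints only, so 2.1 and 5.2 differ.

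**Imaging (5.8).** Follow-up includes "a low-dose CT along with a standing radiograph at the 2-year follow-up".

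**Role of fusion.** The Synopsis, 1.1 and 2.1 all list fusion among the outcomes on which MIS should be non-inferior. In the win-odds hierarchy it is the seventh and last tier, below back pain and SRS-22r.

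**The concern.** The two conditions cover every site that the protocol allows to be prepared for fusion in the MIS arm. They leave out one that it allows in the open arm. A segment that is solidly bridged over laminae or spinous processes, with no facet bridge and no interbody bridge, meets neither condition. A reader who follows the rule must grade it not fused.

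By design this route exists only in the control arm, so the error lowers the control arm's graded fusion rate. In a non-inferiority trial that is the anti-conservative direction. Blinding the reader does not help, because the asymmetry lies in the definition and not in the reading. At stake is whether the fusion result can support the statement that MIS fuses as well as open surgery.

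**Working it through.** The point concerns a definition, so the protocol has no figure of its own to reproduce. The check has three steps.

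**1. Sites side by side**

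| Site | May be decorticated, MIS (5.1) | May be decorticated, open (5.2) | Counts as fusion (2.1 vii, 6.1 item 7) |
|---|---|---|---|
| Facet joints | yes, all or some | yes, all or some | yes (a) |
| Laminae, spinous processes | not named | yes, optional | no |
| Vertebral bodies | not named | not named | yes (b) |

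The mismatch sits in the second row. For any positive rate of laminar-only or spinous-process-only bridging in the open arm, and none in the MIS arm, the graded difference shifts towards MIS.

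**2. Effect on the overall win odds**

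Let r be the share of pairs still tied when tier vii is reached. Let d be the drop in the open arm's graded fusion proportion caused by misgrading alone, with no true difference between the arms. Then

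win odds = (0.5 + r·d/2) / (0.5 − r·d/2).

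The protocol gives neither r nor d; both are assumptions.

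| r | d = 0.10 | d = 0.20 | d = 0.40 |
|---|---|---|---|
| 0.004 | 1.001 | 1.002 | 1.003 |
| 0.05 | 1.010 | 1.020 | 1.041 |
| 0.15 | 1.03 | 1.06 | 1.13 |

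Worked case: r = 0.05 and d = 0.20 give r·d/2 = 0.005, and 0.505/0.495 = 1.02.

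To place r, the seven tiers were simulated with assumed inputs: event rates of 2% to 5%, NRS mean 1 or 2 with SD 2, and SRS-22r total mean 4.1 with SD 0.5. About 0.4% to 0.5% of pairs reached the fusion tier. About 14% to 20% were still tied just before SRS-22r. So r = 0.15 describes a setting in which SRS-22r breaks almost no ties. The non-inferiority limit in 7.1 is 0.60.

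**3. Effect on the fusion comparison itself**

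Here d passes straight through as an apparent MIS advantage. The following is an illustration only. Suppose a healed fusion requires every segment, with 10 segments per patient, and a share q of open-arm segments bridges only over laminae or spinous processes, independently of one another. The share of otherwise fused open-arm patients graded not fused is 1 − (1 − q)^10:

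- q = 1%: 1 − 0.99^10 = 9.6%
- q = 2%: 1 − 0.98^10 = 18.3% (14.9% with 8 segments, 21.5% with 12)
- q = 5%: 1 − 0.95^10 = 40.1%

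Independence is a strong assumption, because one surgeon chooses the decortication for a whole patient. If such segments cluster completely within patients, the affected share falls to q itself: 1%, 2% or 5%.

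**The case against.** The strongest reply is that the definition uses a common yardstick. Permission to decorticate facet joints is identical in the two arms, condition (a) needs only one bridged facet joint per segment, and the same rule is read blind on the same CT. A misgraded segment needs several things together: optional laminar or spinous-process decortication, a solid bridge there, no bridge over either facet joint, and no interbody bridge. Nothing in the protocol says how often that happens. Fusion also has no separate test in this document. It is analysed only as the last tier of the win odds and is not among the secondary variables in 6.2.

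Most of this stands, and it limits the size. It does not close the gap. A yardstick confined to sites common to both arms still omits a bed that one arm may use instead, and the protocol does not say that the restriction is intended. It also names fusion as a non-inferiority aim, so the fusion rates in each arm will be read as evidence on that aim whether or not they are formally tested.

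A reader might infer that open-arm fusion will be understated by tens of percentage points. The documents do not support that: the 9.6% to 40.1% figures rest on assumed rates, on independence, and on an all-segments rule that the text does not spell out. A reader might also infer that laminar bridging cannot occur in the MIS arm. The protocol says only that those sites are not prepared there.

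**Conclusion.** The concern holds as a gap in the definition of one primary-endpoint component, with a known direction and an unknown, possibly low, size. The direction rests on the text of 2.1, 5.1, 5.2 and 6.1 and on the premise that bridging at these sites follows preparation of these sites.

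A reader might go on to infer that the primary non-inferiority conclusion is in danger. It is not, on any plausible inputs. The shift in the win odds is about 0.001 to 0.02 in the likelier cases. It reaches 0.13 only if 15% of pairs get to the last tier and open fusion is understated by 40 points. The practical consequence is confined to the fusion comparison, where any misgrading appears in full as an advantage for MIS. This is a worthwhile, inexpensive improvement and not a defect that undermines the trial.

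**What to change.** - In 2.1 (item vii) and 6.1 (item 7), add a third sufficient condition, applied identically in both arms: *c. Bone bridge between adjacent laminae or spinous processes.* Use the same introductory sentence in both sections.
- Have the blinded CT reader record, for each segment, which of a, b or c is met.
- Report the result under a and b alone as a sensitivity analysis, so that the effect of the added condition is visible.
- Reconcile the control-arm decortication text in 2.1 with that in 5.2.

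Make the change before any 2-year CT is read. With enrolment from mid 2025 (13.1), the first of these scans fall due around mid 2027, so the change can be made without knowledge of outcomes.

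**Cost.** The CT and the reader are already planned; the reading form gains one column. Posterior bridging close to metal is harder to grade on a low-dose CT, which is one reason to keep the two-condition result. Section 11 treats a change in how a primary variable is measured as a substantial amendment, so the Ethical Review Agency must be informed and asked for its opinion or approval first.

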## **2.2 Secondary objectives**

The following secondary objectives will be studied in comparisons between MIS and open operating procedures.

### **Secondary objectives related to the patient**

- Inpatient stay

### **Secondary objectives related to operative technique**

Clinical Study Protocol	Unique protocol ID	MISCOS
	Version No:	1.1
	Date:	2025-09-27

- Deformity correction rate assessed as Cobb-angle correction in a postoperative x-ray from the first standing radiograph compared to the last preoperative radiograph. The correction of the curve will be calculated according to the formula: (preoperative Cobb angle - postoperative Cobb angle) / (preoperative Cobb angle) × 100%.
- Progression of Cobb angle in the operated levels at 2-years standing AP/PA x-ray compared to the 3-month standing AP/PA x-ray.
- Progression of secondary curves at 2 years f-u compared to the 3-month x-ray.
- Perioperative blood loss.
- Technical accuracy of screw placement at first attempt.
- Total procedure time (from incision to closure) as well as normalized to number of spinal levels from the upper to the lower instrumented vertebra.
- Accuracy of screw placement at first attempt (see 6.2)
- Intraoperative neurophysiological monitoring (see 6.2). Any incidences are recorded.

#### Secondary objectives related to patient surgical & postsurgical characteristics

- Postoperative characteristics
  - Costs per patient. Total cost per patient during the first 2 years of the study including cost of possible re-admissions and reoperations related to index surgery. Data on costs on the individual level will be collected. These consist of costs for the inpatient and outpatient visits (including surgery, radiographs, navigation), analgesic and antibiotic treatments as well as possible re-admissions related to index surgery.
- Patient reported outcome measures (see 6.2)

## 3 STUDY DESIGN AND PROCEDURES

### 3.1 Overall study design and flow chart

This is a multi-center parallel assignment two arm randomized controlled trial (Figure 1). The trial will use a pragmatic approach and use existing equipment and document handling at the participating centers. Data from the existing quality registries for spine surgery will be extracted for outcome assessments.

Randomization between the two treatment arms will take place approximately a week preoperatively, as close to the operation day to minimize selection bias. Postoperative, blinding of the patients and health care personnel will be done.

[figure not shown]
The surgeons will be the only personnel related to patient follow-up that will not be blinded. However, the majority of the analyses, all postoperative imaging and record data collection and analysis will be performed by blinded reviewers.

Patient reported outcomes will be assessed without influence of the care giver.

Clinical Study Protocol	Unique protocol ID	MISCOS
	Version No:	1.1
	Date:	2025-09-27

The Uppsala University hospital performs approximately 80 spine deformity surgeries yearly and it is estimated that  $1/4$  of these meet the inclusion criteria for the study. Similar estimations are done for the rest of the centers with a total enrolment of approximately 50 patients per year. Our time plan includes study start (mid 2025), last patient included (2028) and last 2 year follow up (2029). Registry outcome data are collected preoperatively, at 1 year and 2 years. Registry data may also be collected at 5 and 10 years. The study may have come to an end 2038. However, delays in studies such as these are not uncommon.

Figure 1: Flowchart

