## 4.3 Subject enrollment and randomization

Individuals scheduled for spinal deformity surgery will be informed of the study at the time of an outpatient visit.

Subject eligibility will be established before treatment randomization. Subjects will be randomized sequentially approximately a week before operation, as subjects are eligible for randomization. If a subject discontinues from the study, the subject number will not be reused, and the subject will not be allowed to re-enter the study.

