## 5.4 Blinding

The study design does not allow blinding of the surgeons and other personnel in the operating theatre. However, the patient and other health-care personnel will be blinded and held up to two years postoperatively. Patient reported outcomes will be assessed without influence of the caregiver.

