## 5.5 Randomization

The subjects are randomized in a 1:1 ratio, for MIS or open technique treatment arms. Randomization will be performed through the web-based platform of the Swespine registry (or similar platforms like RedCap) using an allocation sequence hidden from the healthcare personnel and provided independent from the study. Block randomization will be used. Block sizes will be unknown for the researchers. The inclusion will end when the sample size has been reached in both intervention arms.

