9. Health economics: Total cost per patient during the first 2 years of the study including cost of possible re-admissions and reoperations related to index surgery. Data on costs on the individual level will be collected. These consist of costs for the inpatient and outpatient visits (including surgery, radiographs, navigation), analgesic and antibiotic treatments as well as possible re-admissions related to index surgery.
10. Patient reported outcome measures. Collected from Swespine or similar platforms after 1, 2, 5 and 10 years.
  - a. SRS-22r: The SRS-22r is a scoliosis specific questionnaire aiming to estimate quality of life in patients with scoliosis [1]. It contains 24 items divided into 5 domains covering function, pain, self-image, mental health, and satisfaction. An index value is calculated for each domain and a total index value is possible to calculate ranging from 1 (worst) to 5 (best).
  - b. EOSQ-24 is a proxy answered questionnaire and will be used in individuals up to the age of 15. It consists of 24 questions of daily function, pain, pulmonary function and mobility [3].
  - c. Oswestry Disability index (ODI) is used in individuals from 15 years and older. ODI is a back specific index measuring disability due to back pain [4]. It is the recommended instrument for studies concerning back pain. An index from 0-100 is calculated. An ODI of 0–20 indicate minimal disability, 21–40; moderate disability, 41–60; severe disability, 61–80; severely crippled, 81–100; bed-bound.
  - d. EQ-5D 3 level is a generic quality of life instrument and consists of five areas reflecting mobility, self-care, usual activities, pain/discomfort and anxiety/depression [5]. Response alternatives range from no problems to extreme problems. An index can be calculated and depending on baseline value set used the index runs between approximately -0.5 (worst possible health) to 1.0 (best possible health). The EQ-5D-3L will be used for health economic analyses. The EQ-VAS is part of the EQ-5D and registers the patient's self-rated health on a visual analogue scale (from 0 to 100; best).

Clinical Study Protocol	Unique protocol ID	MISCOS
	Version No:	1.1
	Date:	2025-09-27

- e. Postoperative pain relief assessed by NRS at discharge. Additionally, given and prescribed doses of analgesics that follow clinical routine protocols will be registered from the hospital files.

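### Section 3.1 places patient blinding after surgery although the arm is allocated about a week before it, and no section keeps patients and families unaware of the arm in between

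*Protocol*

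**What the plan says.** **When the arm is drawn.** Protocol section 3.1: "Randomization between the two treatment arms will take place approximately a week preoperatively". Section 4.3 agrees: "Subjects will be randomized sequentially approximately a week before operation, as subjects are eligible for randomization". A footnote to Table 1 in section 3.2 gives the same timing.

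**When the blind applies.** Directly after its sentence on randomization, section 3.1 states: "Postoperative, blinding of the patients and health care personnel will be done". Section 5.4 says that "the patient and other health-care personnel will be blinded and held up to two years postoperatively". It gives that end but no start.

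**Who is not blinded.** Section 5.4: "The study design does not allow blinding of the surgeons and other personnel in the operating theatre". Neither section mentions parents or guardians.

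**What is concealed.** Section 5.5 describes "using an allocation sequence hidden from the healthcare personnel and provided independent from the study". Section 3.2 says the lists are prepared independently and concealed from the researchers. Both statements concern the list, not the patient's assigned arm.

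**What the blind protects.** Items v and vi of the primary endpoint (section 2.1) are patient-reported at two years: "Assessment of pain at 2 years f-u", by numeric rating scale (NRS), followed by SRS-22r. Enrolment starts at age 10 (section 4.1). Among the secondary variables, "EOSQ-24 is a proxy answered questionnaire and will be used in individuals up to the age of 15" (section 6.2, item 10b).

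**The concern.** For about a week the arm exists and the surgeon may know it, while the only statement on when blinding takes place puts it after the operation. Nothing tells a site to keep the arm from the patient or the family during that week. Disclosure then would be consistent with section 3.1 and would not count as a deviation.

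What is at stake is the credibility of the self-reported tiers. A patient who knows that he or she had the newer, less invasive operation may rate pain and quality of life more favourably. In a non-inferiority comparison that shift works towards the claim. The sponsor chose to blind patients for two years, so protecting self-report is its own aim. The text as written does not secure it.

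This is not something to leave to a statistical analysis plan. Who is kept unaware, from when and until when, is a matter of site conduct, and an analysis cannot recover a lost blind.

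**Working it through.** The protocol states no figure on this point, so the main check sets the sections side by side.

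| Time | What the protocol provides | Patient or family kept unaware of the arm? |
|---|---|---|
| Before randomization | Lists and sequence concealed (3.2, 5.5) | Not applicable, no arm yet |
| Randomization to surgery, about one week | 3.1 places blinding after surgery; 5.4 gives no start | Not stated for the patient in 3.1; open in 5.4; parents named nowhere |
| Surgery to two years | Patients and other health-care personnel blinded (3.1, 5.4) | Patient yes; parents not named |
| Two-year questionnaires | Blind runs up to two years (5.4) | Probably included, but not tied to return of the forms |

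1. **Start.** If section 5.4 is read as blinding from allocation, it conflicts with section 3.1. If section 3.1 governs, the week before surgery is uncovered. Either way a single start has to be stated.
2. **Concealment does not fill the gap.** A hidden sequence prevents prediction of the next assignment. It does not govern who is told the assignment after it is drawn.
3. **Parents.** The protocol does not say who the EOSQ-24 proxy is; a parent or guardian is the natural assumption. An informed proxy would rate that secondary outcome unblinded. For the primary tiers the route is indirect: a parent who knows the arm may tell the child.

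**Direction of a bias, for illustration only.** All inputs here are assumptions.

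- e = share of patients per arm with an event in tiers i to iv, taken as 5%, 10% or 15%.
- d = net shift in self-report towards minimally invasive surgery, in standard deviations, applied to the whole arm.
- Scores are continuous and free of ties, and the true win odds is 1.0.

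The share of pairs in which neither patient has such an event is (1 − e)²: 0.95² = 0.902, 0.90² = 0.810, 0.85² = 0.722.

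Win probability = 0.5 + (1 − e)² × (Φ(d/√2) − 0.5). Win odds = win probability / (1 − win probability).

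Example with e = 10%, d = 0.2: Φ(0.1414) = 0.5562; 0.5 + 0.810 × 0.0562 = 0.5455; 0.5455/0.4545 = 1.200.

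| d | e = 5% | e = 10% | e = 15% |
|---|---|---|---|
| 0.1 | 1.107 | 1.096 | 1.085 |
| 0.2 | 1.226 | 1.200 | 1.177 |
| 0.3 | 1.357 | 1.315 | 1.276 |

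The table shows that a shift in self-report reaches the win odds largely undiluted, because under these event rates 72% to 90% of pairs pass to the questionnaire tiers. If only some patients learn the arm, the excess of the win probability over 0.5 shrinks in proportion.

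**The case against.** - **Start.** The sentence in section 3.1 leads into remarks on personnel involved in follow-up, so it may only describe who is blind during follow-up. Section 5.4 can be read as blinding from allocation. A reader might infer that patients will be told their arm before surgery; no section says so. This stands as far as it goes: the defect is a rule that permits disclosure, not one that prescribes it. The two sections still need one start.
- **End.** A reader might infer that the blind lapses before the primary questionnaires are answered. The text does not support that. The two-year limit and the two-year assessment coincide, and nothing provides for disclosure before the forms are returned. Stating the end is a clarification.
- **Parents.** A reader might infer that unblinded proxies enter the primary analysis, or that the promise of assessment free of caregiver influence is broken. EOSQ-24 is in none of the seven primary tiers, and in context caregiver most naturally means the clinician. Nor does the protocol say that forms are completed at home; its note on web or paper collection names SRS-22r and other questionnaires but not the pain scale. Consent pages are not available, so what families are told cannot be judged.
- **Size.** A reader might take the illustrative win odds as evidence of a raised false-claim rate. They are not. They start from a true win odds of 1.0, where a non-inferiority claim against the 0.60 limit of section 7.1 would be correct, and they apply an assumed shift to a whole arm.

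**Conclusion.** The point holds for the start of the blind. Section 3.1 places patient blinding after surgery, the arm exists about a week earlier, section 5.4 gives no start, and the concealment statements cover only the lists and sequence. Followed as written, the protocol allows patients and families to learn the arm before surgery, which would defeat the two-year blind protecting the NRS pain and SRS-22r tiers.

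Any resulting bias would probably favour minimally invasive surgery. That rests on the assumption that patients expect the less invasive operation to be better. Its size cannot be estimated from the protocol, which gives neither component event rates nor any indication of how many patients would learn their arm. Leaving parents unnamed is a secondary gap, and the end of the blind needs only clarification. The correction should be made because it is almost free and a lost blind cannot be repaired later.

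**What to change.** Reconcile sections 3.1 and 5.4 to state one group and one window:

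- **Who:** patients, their parents or guardians, and all staff outside the operating team.
- **From:** randomization, with the allocation released only to the operating team.
- **Until:** that patient's two-year questionnaires have been returned.

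The patient's blind need not also wait for the two-year CT, because section 3.1 already assigns postoperative imaging to blinded reviewers.

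The change adds no visits and leaves treatment as it is. Its costs are that surgeons must keep to neutral wording with families before surgery, and that patients who return their two-year forms late learn their arm somewhat later.
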